### ii. Randomization process

Participants will be randomized to one of four groups. This design allows for a rolling admission and increased contemporary controls in the event a device is not available at the time of enrollment. The conditions subjects are randomized to may vary depending on product availability. Within each group, we will also randomize the patients to sequence the right or left lung for the baseline bronchoscopy in an approximate 1:1 ratio. These patients will then receive a second bronchoscopy in the opposite lung at ~71 days in order to reduce the influence of the baseline procedure at follow-up. The randomization procedures will be supervised by the biostatistician.

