## **b. Participant Selection**

### **Eligibility Criteria**

- Male or female subjects who are age 21-52\*;
- Smokers who smoke  $\geq 5$  filtered cigarettes/day for  $\geq 1$  year\*;
- No unstable or significant medical conditions as determined by medical history (see exclusion criteria below) to ensure safety of the subject, to minimize the effects of poor health on biomarker measures and to maximize compliance to study procedures);
- Negative COVID-19 test (if applicable)\*\*;
- Subject has an electronic device and is willing to download the iCO app to report exhaled CO level daily;
- Able to read adequately to complete the survey and related study documents or give consent; and,
- Subject has provided written informed consent to participate in the study.

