All statistical analysis and visualization of differential methylation will be performed using Partek Genomics Suite (Partek). Raw intensity data (idat files) will be imported into Partek and normalized using the Subset-quantile Within Array Normalization (SWAN). Any probes with detection  $P > 0.05$  and probes in Y- chromosome to avoid sex-specific methylation bias will be filtered out before further analysis. To identify differentially methylated CpGs, methylation  $\beta$ -values will be converted to M-values by logit-transformation for the statistical modeling purpose. For preliminary identification of patterns in DNA methylation, unsupervised hierarchical clustering among the groups of samples will be performed. The Euclidian distance among the groups of samples will be calculated by the average linkage. In order to assess variance among samples, Principal Component Analysis (PCA) will be done. To characterize the methylation patterns, differentially methylated CpGs will be classified by enhancer, CpG island or its neighbors [2 kb regions upstream and downstream of the CpG islands (shores) or 2 kb regions upstream and downstream of the CpG island shores (shelves)] and functional promoters [within 1500 bp of a transcription start site (TSS) (TSS1500), within 200 bp of a TSS (TSS200), 5' untranslated regions (5'UTR), first exon (1stExon)], and other regions (body, 3'UTR, or intergenic). Separately, we will also analyze for DNA methylation levels of miRNAs promoter regions to investigate if miRNAs methylation appears to be altered between the groups. When we have a full sample, multiple testing corrections will be performed using the Benjamini and Hochberg False Discovery Rate (FDR with significantly differential methylation levels defined at corrected  $P < 0.05$ ). Genes corresponding to differentially methylated CpGs will be used for identification of gene networks and biological pathways using the Ingenuity Pathways Analysis. In addition, we will examine differences in methylation for candidate genes that have been previously shown to be associated with lung cancer and/or with smoking using the same methods. To understand the potential biological contribution of differentially methylated CpGs to coding gene or miRNA expression (from on-going pilot study), we will correlate between the differentially methylated CpGs (M-value) from the EPIC methylation array and matched coding gene or miRNA expression (log2 transformed intensity) from the Affymetrix Human Transcriptome array or Affymetrix GeneChip miRNA array using Spearman correlations. To determine if differences in DNA methylation are associated with cytokines levels (as measured for IL-6, IL- 10, TNF-alpha, and TNF-alpha in BAL in the current on-going study), we will select CpGs corresponding to IL-6, IL- 10, and TNF-alpha from the EPIC methylation array (targeted analysis) and correlate between methylation levels and corresponded cytokines. Correlations controlling for possible confounders (e.g., age) will be explored using multiple linear regression models. We will also explore if the correlation between methylation and cytokine levels may be mediated by gene expression of cytokines using interaction analysis.

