For methylation, raw intensity data (idat files) will be normalized using the Subset-quantile Within Array Normalization (SWAN). Any probes with detection P > 0.05 and probes in Y-chromosome to avoid sex-specific methylation bias will be filtered out before further analysis. To identify differentially methylated CpGs, methylation β -values will be converted to M-values by logit-transformation for the statistical modeling purpose. For preliminary identification of patterns in DNA methylation, unsupervised hierarchical clustering among the groups of samples will be performed. The Euclidian distance among the groups of samples will be calculated by the average linkage. In order to assess variance among samples, Principal Component Analysis (PCA) will be done. To characterize the methylation patterns, differentially methylated CpGs will be classified by enhancer, CpG island or its neighbors [2 kb regions upstream and downstream of the CpG islands (shores) or 2 kb regions upstream and downstream of the CpG island shores (shelves)] and functional promoters [within 1500 bp of a transcription start site (TSS) (TSS1500), within 200 bp of a TSS (TSS200), 5' untranslated regions (5'UTR), first exon (1stExon)], and other regions (body, 3'UTR, or intergenic). Separately, we will also analyze for DNA methylation levels of miRNAs promoter regions to investigate if miRNAs methylation appears to be altered between the groups. When we have a full sample, multiple testing corrections will be performed using the Benjamini and Hochberg False Discovery Rate (FDR) with significantly differential methylation levels defined at corrected P < 0.05. Genes corresponding to differentially methylated CpGs will be used for gene networks and biological pathways using the Ingenuity Pathways Analysis. In addition, we will examine differences in methylation for candidate genes that have been previously shown to be associated with lung cancer and/or with smoking using the same methods. To understand the potential biological contribution of differentially methylated CpGs to coding gene or miRNA expression (from on-going pilot study), we will correlate between the differentially methylated CpGs (M-value) from the EPIC methylation array and matched coding gene or miRNA expression (log2 transformed intensity) from the Affymetrix Human Transcriptome array or Affymetrix GeneChip miRNA array using Spearman correlations. To determine if differences in DNA methylation are associated with cytokines levels (as measured for IL-6, IL- 10, TNF-alpha, and TNF-alpha in BAL in the current on-going study), we will select CpGs corresponding to IL-6, IL- 10, and TNF-alpha from the EPIC methylation array (targeted analysis) and correlate between

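### The methylation probe filter drops the Y chromosome to avoid sex bias but keeps the X, so the unsupervised displays and a narrow set of X-linked correlations can still reflect sex

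*SAP*

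**What the plan says.** The methylation paragraphs of SAP item 2 set two probe filters. One removes probes with a detection p-value above 0.05. The other is the Y-chromosome rule: "probes in Y-chromosome to avoid sex-specific methylation bias will be filtered out before further analysis". Protocol section 4.g.i (Data Analysis Plan) repeats it, with the same reason: "chromosome to avoid sex-specific methylation bias will be filtered out before further analysis". X-chromosome probes are mentioned in neither document, so they stay in.

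The sample is mixed. Eligibility reads "Male or female subjects who are age 21-52", and the randomisation section states "Participants will be randomized to one of four groups" without stratification by sex.

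Three steps follow the filter with no sex term:
- clustering: "unsupervised hierarchical clustering among the groups of samples will be performed";
- PCA: "In order to assess variance among samples, Principal Component Analysis (PCA) will be done";
- Spearman correlation of methylation with expression: "we will correlate between the differentially methylated CpGs (M-value) from the EPIC methylation array and matched coding gene or miRNA expression".

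At the end of item 2, regression control of the correlations is only to be explored, and age is the one example given. Sex does appear elsewhere: gender is among the possible covariates of the arm-comparison GLMs (item 2), and the baseline dose-response models adjust for sex and age (item 8).

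**The concern.** The rule gives its own purpose, which is to take out methylation that differs by sex. In a sample of men and women the Y chromosome is only part of that signal. In women one X chromosome is inactivated and heavily methylated; in men none is. This is general biology and is not stated in the documents. Removing Y alone therefore leaves a block of probes that move together by sex.

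Unsupervised methods respond to whatever moves many probes together. If a leading component or the first split of the dendrogram separates men from women, it takes up space in the display meant to show methylation patterns between the groups. In the unadjusted Spearman step, a CpG and a transcript that both differ by sex will correlate even if they are unrelated within each sex. DNA methylation is listed among the primary outcomes in protocol sections 1 and 2, so the platform is not peripheral, although these particular steps are exploratory.

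**Working it through.** The plan states no figure on this point, so there is nothing to reproduce. The checks use the SAP's analysed numbers (21 per group, 84 in all, 42 in a pairwise comparison). All else is assumed: half the subjects are women, within-sex SD is 1, 1 to 3% of probes are shifted by sex, and the shift is 1 or 3 SD.

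**PCA.** Simulated matrices had 84 subjects and 10,000 probes, 10 runs per setting, with and without one competing non-sex factor (loading 0.5 SD on 20% of probes). The variance that sex adds along its own direction is k × d²/4, where k is the number of shifted probes and d the shift in SD. The competing factor adds 2,000 × 0.5² = 500. Entries are mean absolute correlations with sex.

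| Shifted probes | d | k × d²/4 | No competing factor: PC1 | Competing factor: PC1 / PC2 |
|---|---|---|---|---|
| 1% | 1 | 25 | 0.87 | 0.07 / 0.88 |
| 2% | 1 | 50 | 0.97 | 0.10 / 0.96 |
| 3% | 1 | 75 | 0.98 | 0.08 / 0.98 |
| 1% | 3 | 225 | 1.00 | 0.17 / 0.97 |
| 2% | 3 | 450 | 1.00 | 0.58 / 0.69 |
| 3% | 3 | 675 | 1.00 | 0.98 / 0.14 |

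The pattern follows the variances. Sex is PC2 while its term is well below 500, mixes across both components at 450, and becomes PC1 at 675. With no sex-shifted probes kept, the correlations of PC1 to PC3 with sex fall to 0.06–0.12. The chance level at n=84 is about √(2/π)/√83 = 0.09.

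**Spearman correlation through sex alone.** If a CpG is shifted by d₁ and a transcript by d₂, with no link within sex and half women, the induced (Pearson) correlation is d₁d₂/√[(d₁²+4)(d₂²+4)]. The simulated columns give the mean Spearman rho and the rejection rate at 0.05 over 2,000 runs.

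| d₁, d₂ | Formula | n=42 | n=84 |
|---|---|---|---|
| 0, 0 | 0 | 0.00; 5.0% | 0.00; 4.8% |
| 1, 1 | 1/5 = 0.20 | 0.20; 24.5% | 0.20; 44.0% |
| 3, 1 | 3/√65 = 0.37 | 0.37; 70.3% | 0.38; 95.2% |
| 3, 3 | 9/13 = 0.69 | 0.68; 100% | 0.69; 100% |

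If either shift is zero, the formula gives zero. These rates apply only to a pair in which both members differ by sex. They are not conditional on the CpG having first been declared differentially methylated.

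**Arm comparison.** SAP Model 1 (item 3) was simulated for a sex-shifted probe with no arm effect: 21 versus 21, baseline to follow-up correlation 0.5 within sex, 4,000 runs, test at 0.05.

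| d | Type I error, sex not in model | Sex in model |
|---|---|---|
| 0 | 0.052 | 0.053 |
| 1 | 0.049 | 0.047 |
| 3 | 0.046 | 0.048 |

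Monte Carlo standard error is √(0.05 × 0.95/4,000) = 0.003, so all values agree with 0.05.

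**The case against.** The strongest reply is that nothing confirmatory is touched. Arms are randomised, Model 1 adjusts for each subject's own baseline value, and item 2 brings gender into the GLMs when it is associated with the biomarker, which a strongly sex-dependent CpG would be. The type I error results support this, and it stands in full.

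A reader might infer that CpG correlations in general are driven by sex. The documents do not support that. The expression correlations use only differentially methylated CpGs and their matched gene or miRNA, and a pair is affected only if it is X-linked and both members differ by sex. The cytokine correlations use only CpGs of IL-6, IL-10 and TNF-alpha, which lie on autosomes (again general biology). Item 2 also foresees some confounder adjustment of the correlations, though it is exploratory and does not name sex.

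A reader might also infer that a chance sex imbalance would pass for an arm effect. If half the subjects are women, two arms of 21 differ by 4 or more women with probability 0.28. That is true of any unstratified binary covariate with that split. Item 2 describes PCA on data from the different visits, so a sex split would already show at baseline, before treatment, and recorded demographics would identify it. No exclusion or decision rule depends on the plots.

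Finally, sex need not be PC1: with another strong source of variation it is usually PC2. What remains is that the filter does not do what it says, and no other provision removes X probes or puts sex into these steps.

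**Conclusion.** The point holds in a limited form. As written, the Y-only filter does not remove sex-specific methylation in a mixed-sex sample. Under the assumed ranges, sex dominates one of the first two components in most settings and is shared between them in one. Unadjusted Spearman correlations can be spurious for the narrow subset of X-linked differentially methylated CpGs whose matched transcript also differs by sex. For such pairs the false-positive rate at 0.05 could run from 24% to 100% at n=42 and from 44% to 100% at n=84.

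These sizes rest on assumptions about X-probe share, sex shift and sex split that the documents do not supply, and on the general fact that X methylation differs by sex. The Model 1 arm comparisons, the targeted cytokine correlations, and the stated sample size, power and alpha are unaffected. This is a cheap correction to exploratory steps on a platform listed among the primary outcomes, not a threat to the trial's inference.

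**What to change.** Make three small edits to SAP item 2, matched in protocol section 4.g.i, before the methylation data are analysed:

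1. Remove X- as well as Y-chromosome probes before the methylation clustering and PCA.
2. Keep X-linked CpGs in the differential testing with sex as a covariate, or analyse them separately within sex. Dropping them there would discard CpGs from a comparison that is not biased.
3. Name sex beside age as an adjustment variable for the CpG-expression correlations.

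The cost is about one line of SAP text and code. The downside is that X-linked CpGs leave the unsupervised displays and need their own sex-adjusted analysis.

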Inflammatory cell infiltrates: Using bronchoscopy, it has been determined smoking increases total cell counts, macrophages, lymphocytes, neutrophils, eosinophils and basophils, by as much as 8-10 fold [45, 46, 54, 56-61, 66, 67]. For example, 132 smokers and 295 never-smokers who underwent bronchoscopy had increased numbers of inflammatory cells in BAL samples, with a dose-response depending on smoking level [39]. Bronchial biopsies show similar results, e.g., 45 asymptomatic smokers compared to never-smokers had statistical increases for neutrophils, eosinophils, mast cells, and macrophages, with means differing 2-4 fold [59]. Important evidence comes from smoking cessation studies, where 28 smokers who underwent bronchoscopy at 12 months after quitting showed decreases of inflammatory cells compared to non-quitters [40]. Directly relevant to this application, it has been reported that sputum neutrophils statistically decreased after 6 weeks of smoking cessation in three studies [68-70], although a small sputum study did not find similar results after 4 weeks [71]. Sputum macrophages decrease as early as one week in sputum after quitting [70]. Also, there are reported decreases of pulmonary macrophages and neutrophils with smoking reduction of more than 50% [72].

Inflammatory cytokines: Lung cytokines affected by smoking (e.g., IL6, IL8, IL10, IL33, TNF- $\alpha$ ) are associated with COPD and lung cancer [32, 54, 55, 61, 73-79]. For example, a bronchial biopsy study of 45 asymptomatic smokers and never-smokers showed statistical increases for smokers of IL-8, with means that are 2-4 fold different [59]. In another study using bronchial biopsies and immunohistochemistry of 47 subjects, IL6 was associated with smoking [79]. Inflammatory cytokines, such as IL8, are higher in patients with emphysema [73]. While one study reported that there was no difference between smokers and non-smokers for IL6 and IL8 in a

cross-sectional analysis [80], a smoking cessation study showed statistically significant reductions at 12 months for IL8 [54]. The repeatability and reliability of repeated measures for BAL cytokines has been demonstrated, but it also should be noted that blood cytokines are not a good surrogate for lung cytokines [67].

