**The Effects of a Standardized Research E-Cigarette on the Human Lung:
A Clinical Trial with Bronchoscopic Biomarkers**

NCT03691350

Statistical Analysis Plan, 09/19/22

SREC SAP

The Specific Aim for this two year project is:

To assess inflammatory changes over 10 weeks (8 weeks experimental condition) for lung and urine biomarkers in smokers in a clinical trial where smokers are randomized to: continued use (n=32), complete switching to the nicotine standardized research electronic cigarette (SREC) (n=32), complete switching to the placebo SREC (n=32), or complete switching to nicotine replacement therapy (NRT) (n=32).

- 1) We will enroll 128 subjects (32 per group). For power calculations, we will use a conservatively planned 66% retention rate at 5 weeks, knowing that we have a 100% retention for never smokers receiving serial bronchoscopies. Thus, the final sample size will be 21 subjects per group (n=84). Although we expect a higher retention rate, we assume 66% to ensure that we have the minimal numbers required to reach meaningful conclusions. Since follow-up samples would not be obtained from subjects that do not finish the treatment protocol, and these samples (inflammation/omics) are our primary outcomes, we cannot use an 'intent to treat' strategy since dropouts will have missing outcome data for any analyses including follow-up measurements (the primary Aim). In light of this, we will compare dropout rates between arms and with demographic/clinical to ensure that the analyses results are not biased by unbalanced dropouts. We will also test for differences in baseline molecular measurements between subjects that dropout after baseline samples are taken vs. subjects that complete the protocol. While we will make every effort to minimize the missing data for this study, missing data can arise due to various reasons. Violation of missing completely at random (MCAR) will be checked by evaluating whether any covariates are associated with missing data. If so, these covariates will be subsequently included and controlled for in the GL(M)M models. In addition, sensitivity analyses will also be conducted using results from multiple imputation.

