The 'omics' (miRNA, mRNA and metabolomics) analysis and visualization of the data will be performed in the R statistical language. Data will be log2-transformed and normalized using either quantile normalization for gene expression (miRNA and mRNA) or TIC/MSTUS normalization for metabolomics. Unsupervised clustering analysis, including PCA and hierarchical clustering will be performed to visualize natural clusters in the dataset and evaluate data quality. Multiple testing corrections using the Benjamini and Hochberg False Discovery Rate (FDR) will be performed. Significantly altered genes and metabolites will be defined as those with FDR corrected p-value < 0.05 and fold changes > 2 or > 1.5, respectively. Identified genes or metabolites will be used to identify relevant networks and pathways using Ingenuity Pathways Analysis. For gene expression, we will further study associations between miRNA-mRNA pairs based on publically available target prediction databases such as TargetScanHuman, miRDB, miRWalk2.0 and others. Global integrative analysis, through correlations, will be performed using Partek software.

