Power is provided for a t-test [2]. Expression/metabolomics/proteomics data tend to follow Gaussian distributions, although there can be violations within each platform. With the large number of variables present in 'omics data, it is intractable to evaluate the appropriateness of the model for each individual variable. Therefore, we use the overall distribution across all variables within a platform to assume a distribution. While individual variables may randomly deviate from the model assumptions (normality, in most cases), if the overall distribution is Gaussian we assume that each of the features was sampled from the overall Gaussian. However, to check if assumptions are causing spurious positive results, we will test each associated feature, post hoc, for departures from the model assumptions. Cell counts were also considered Gaussian for these power calculations. While counts are inherently discrete, because the expected cell counts are very large ($>2E+07$), Gaussian should be a good approximation for this distribution. The parameters included in the power calculation are the CVs, the p-values, and the effect sizes. The CVs used were estimated from preliminary data (and similar data from other studies). The effect sizes assumed are reasonable (smaller) compared to the effect sizes we see in the preliminary data. The p-values used were stringent to adjust for multiple comparisons. Because, especially with 'omics data, we do not know a priori the number of tests, we use significance thresholds that correspond to an expected number of false discoveries per number of tests to control for multiple comparisons without defining the number of tests. For the primary analyses, we accept that one expected false discovery per 10,000 tests is a reasonable error rate. In practice, we will use FDR to determine the expected fraction of false discoveries for assuming a particular significance threshold. For a final sample size of 21 in the control group and 21 in each use condition, for a two-sided analysis, we have 80% power to detect ≥ 1.5 -fold difference in cell counts/cytokine levels between each condition and controls for a two-sample t-test. For gene expression/metabolomics data, with the same considerations except a CV=0.5 (approximate from many gene expression data sets with which we have worked), we have 80% power to detect ≥ 2.1 -fold differences.

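### Methylation of bulk airway brushings is analysed with no account of cell mix, so a shift in leukocyte fraction could be read as epigenetic or gene regulation

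*SAP*

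**What the plan says.** Protocol 4.c.i (bronchoscopy and brushing procedure) collects four to five brushings of main-bronchus epithelium into one tube. Protocol 4.d.iii takes total RNA and total DNA from brushings for the expression and EPIC methylation arrays, and Table 3 lists both under bronchial and nasal brushing. No cell sorting is described. Differential counts and CyTOF are listed for lavage only.

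Model 1 in SAP item 3 regresses the follow-up measure on the baseline measure and arm. SAP item 2 adds batch and other associated variables, with baseline smoking, FTND and gender as examples. For the methylation correlations the only example of a confounder is age.

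CpGs are called at FDR-corrected P < 0.05, with no effect-size floor. Then "Genes corresponding to differentially methylated CpGs will be used for gene networks and biological pathways using the Ingenuity Pathways Analysis". The same CpGs are correlated with gene and miRNA expression, and CpGs in cytokine genes are correlated with lavage cytokines. Expression has a stricter rule, FDR below 0.05 and a fold change above 2, before "Identified genes or metabolites will be used to identify relevant networks and pathways using Ingenuity Pathways Analysis".

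On expected cell changes, Protocol section 2 hypothesises less lung toxicity after switching, and section 3 plans to monitor cell counts for a reduction. Section 3 also cites a 2-4 fold difference in airway-wall cells: "Bronchial biopsies show similar results, e.g., 45 asymptomatic smokers compared to never-smokers had statistical increases for neutrophils, eosinophils, mast cells, and macrophages".

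**The concern.** A bulk measurement is an average over the cell types in the sample, weighted by their fractions. If leukocytes and epithelium differ at a CpG, a change in the leukocyte fraction moves the bulk value even when no cell has changed. A trial designed to detect a fall in inflammatory cells has a particular reason to check this.

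Two outputs are exposed. Differentially methylated genes and pathways could reflect fewer leukocytes in the brush and be described as altered regulation. CpG-expression and CpG-cytokine correlations could arise because both features follow the same fraction. An arm term does not remove the second problem, because the fraction also varies between people within an arm. DNA methylation is among the primary outcomes listed in Protocol sections 1 and 2, so how it is interpreted matters.

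**Working it through.** **Step 1: the plan's own figure.** The SAP's error rate is "we accept that one expected false discovery per 10,000 tests is a reasonable error rate", i.e. alpha = 0.0001, with this sample: "For a final sample size of 21 in the control group and 21 in each use condition, for a two-sided analysis" (66% of 32 = 21.1). For gene expression with CV 0.5 it states "we have 80% power to detect ≥ 2.1 -fold differences". On the log scale, SD = sqrt(ln(1 + 0.5²)) = 0.472. A two-sample t-test with 21 per arm has 80% power at 2.14-fold. For cell counts (CV 0.26, SD 0.256) the figure is 1.51-fold. These agree with the stated 2.1 and 1.5, so I use the same test, sample size and alpha below.

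**Step 2: methylation with a change in cell mix only.** The documents give no leukocyte fraction for brushings and no M-value SD, so these inputs are assumptions:
- CpG 20% methylated in epithelium and 80% in leukocytes
- leukocyte fraction 10% in controls and 6% in switchers, SD 3 points
- assay SD 1 point of beta
- no change within any cell

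Bulk beta = 0.2 + 0.6 × fraction, which gives 0.260 and 0.236. M = log2(beta/(1 − beta)) gives −1.509 and −1.695, a shift of 0.186.

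The fraction SD contributes 0.6 × 0.03 = 0.018 to beta and the assay 0.010. Dividing by beta(1 − beta)ln 2 and combining gives M-value SDs of 0.154 and 0.165, or 0.160 pooled. The noncentrality is 0.186/(0.160 × sqrt(2/21)) = 3.77. An independent residual M-value SD for other between-person variation then enlarges the pooled SD:

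| Residual M-value SD | Pooled SD | p<0.05 | p<0.01 | p<0.0001 |
|---|---|---|---|---|
| 0 | 0.160 | 96% | 85% | 32% |
| 0.2 | 0.256 | 63% | 37% | 4% |
| 0.3 | 0.340 | 41% | 19% | 1% |
| 0.5 | 0.525 | 20% | 7% | 0.2% |

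Simulation agrees with each row. For a fall from 10% to 8% only, the p<0.0001 chance is 1.5% with no residual variation and 0.1% at SD 0.3. For the same proportional fall from 2% (to 1.2%, fraction SD scaled) it is 0.5% with no residual variation.

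A sharper CpG gives larger figures. With 10% methylation in epithelium, 90% in leukocytes, fraction CV 0.26 and a halving from 10%, the chance at 0.0001 is 83%, 42%, 7% and 1% at residual SDs of 0.2, 0.3, 0.5 and 0.8. From a starting fraction of 2% it is 1% or less at SD 0.3, even for a 2.5-fold fall.

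These t-tests omit the baseline covariate of Model 1, which would lower the residual SD by an unknown amount.

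**Step 3: expression.** For a transcript found only in leukocytes, the bulk fold equals the fold change in the fraction: 10/6 = 1.67, or 10/8 = 1.25. Neither passes the fold>2 rule. After a 2.5-fold fall from 10% to 4%, a gene 100 times higher in leukocytes changes by (10 + 0.90)/(4 + 0.96) = 2.20-fold and passes. A gene 20 times higher changes by (2 + 0.90)/(0.8 + 0.96) = 1.65-fold and does not.

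**Step 4: correlations.** In the Step 2 example the fraction explains 1.8²/(1.8² + 1²) = 76% of the variance in beta. Suppose it also explains 30% of an unrelated gene's variance. The induced correlation is sqrt(0.76 × 0.30) = 0.48 (0.47 on the M scale). This is significant at 0.05 in about 90% of trials when two arms (42 samples) are pooled with arm removed, and in about 60% for one arm of 21. At a residual SD of 0.3 the fraction's share drops to 0.135²/0.337² = 16%, and the correlation to sqrt(0.16 × 0.30) = 0.22.

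**The case against.** The strongest reply is that the premise about brushings is not documented. The brush targets grossly normal epithelium, the 2-4 fold figure comes from biopsies of smokers against never-smokers, and the trial's own cell counts are made on lavage. That stands. It limits the claim to what could happen if the brushing fraction shifts, and it is also a reason to estimate the fraction.

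A reader might infer that the randomised methylation comparison is biased. The documents do not support this. Cell mix is a post-randomisation quantity, and the arm effect on bulk tissue is a valid total effect. A reader might also infer that pathway findings would merely restate the cell-count outcome, but that outcome is measured in a different compartment.

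Extending the point at full strength to differential expression is not supported either, because the fold>2 rule blocks it unless the fraction falls more than 2-fold and the gene is expressed almost only in leukocytes.

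The covariate clauses are open lists and could admit a cell fraction, and the SAP speaks only of a potential contribution of CpGs to expression. However, a fraction that no one plans to derive cannot enter a model, and cautious wording does not separate the two explanations.

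**Conclusion.** The omission is real and worth correcting. It concerns interpretation and does not threaten the validity of the trial. Methylation is the more exposed because its call rule has no effect-size floor; the CpG-expression and CpG-cytokine correlations are exposed because a shared fraction can produce them; differential expression is partly protected.

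The size cannot be fixed from the documents. It depends on the starting leukocyte fraction, the fall by arm, the CpG's contrast between cell types and the residual M-value SD, all assumed here. In the main example the chance at 0.0001 runs from about 32% with no other between-person variation to about 1% or less at a residual SD of 0.3 or more. It is small if leukocytes are only a few percent of the brushing. The figures at 0.05 and 0.01 should not be taken as the plan's error rate, since it calls CpGs by FDR and plans power at 0.0001.

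**What to change.** Add to SAP item 2, before the methylation data are examined by arm:

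1. Estimate cell fractions for each bronchial and nasal brushing from the planned EPIC data, by a named reference-based or reference-free method.
2. Compare the fractions by arm and report them.
3. Report differential methylation and its pathway analysis twice, side by side: unadjusted (total effect) and composition-adjusted. Keep the unadjusted result as the main arm comparison, and label features that do not survive adjustment as possible cell-mix effects.
4. Include the fractions as covariates in the CpG-expression and CpG-cytokine models.

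Pathway analysis should not be restricted to features that survive adjustment. Adjustment conditions on a post-randomisation variable and may remove real effects acting through cell mix. The fractions are also estimated with error: in simulation, a fraction known exactly brings rejection at 0.05 back to about 4-7%, but an estimated one will do less.

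The cost is analysis time. No new visit, procedure or sample is needed.
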